Evaluation of Hemorrhage Control and Tourniquet Training Effectiveness for Laypersons: TRIAGE
Study (**TouRnIquet trAininG Effectiveness**)

April 3, 2018
Study Protocol and Statistical Analysis

- 1) **Study design:**
 - a) Prospective open-label trial

- 2) **Consent:**
 - a) Verbal consent

- 3) **Protocol:**
 - a) All participants will receive the ACS stop the Bleed training from qualified instructors. This training is 45 to 60 minutes long, consisting of an audio-visual presentation with tourniquet application instructions followed by hands-on training under the supervision of an instructor. The training takes place in groups of 20 to 50 at a time. The audio-visual part of the training takes place in groups of 20, which are then divided into subgroups of 4-8 for hands-on training with an instructor. There is no compensation for the study participants.
 - b) The evaluation of hemorrhage control competence will take place individually. A mannequin, the Hapmed tourniquet trainer, with a traumatic amputation of the leg just above the knee will be present. A reviewer will provide instructions, including that the lights on the leg represent continued bleeding and they will have a maximum of 2 minutes to apply the tourniquet. The participant will be provided a tourniquet and told to stop the simulated bleeding. Participants will be tested in all 5 types of tourniquets sequentially using the same method but with the order of testing varying according to the randomization. The reviewer will start timing after telling the participant to begin. This will then be repeated for the other type of tourniquet the individual will need to apply. No feedback will be given to the participant throughout the testing process.
 - i) Supplies for the improvised tourniquet will include a T-shirt, long stretch of gauze, a stick to act as a windlass, and a leather belt
 - c) Parameters measured:
 - i) The participants will be timed until they feel that they have stopped the bleeding or they tell the instructor they are done. The maximum amount of time provided to apply the tourniquet will be 2 minutes based on the results of the investigators' prior studies in which the 90th percentile for time to correct application was 117 seconds.
 - ii) Appropriateness of hemorrhage control will be determined by correct placements of tourniquet as defined by at least 2 inches proximal to the amputation site

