 - iii) Adequate pressure to stop the bleeding which will be set at 250 mmHg. For unsuccessful hemorrhage control, the reason for failure will be recorded.
 - iv) Correct tourniquet application defined by:
 - (1) Time to application < 120 seconds
 - (2) Placement of tourniquet a minimum of 2 inches proximal to amputation
 - (3) Tourniquet application pressure > 250 mmHg
 - d) All the reviewers would be physicians, nurses and EMTs, trained in hemorrhage-control. The complete test for each individual will not take more than 15 mins.

- 4) **Randomization for the order of tourniquet application:**
 - a) Permutated block randomization will be used to vary the order for application of the 5 different types of tourniquets (CAT, RAT, SWAT-T, Sof-T, and improvised tourniquet)

5) Pre-trial questionnaire:

- a) Study subjects will be given a pre-trial questionnaire to gather information regarding age, gender, and level of education. The questionnaire will also include questions to assess their knowledge regarding hemorrhage control and to determine their willingness and self-reported comfort level in acting as a first-responder in a mass casualty scenario. Answers will be presented on a Likert-type scale or dichotomous yes-no.

6) Post-trial questionnaire:

- a) After the hemorrhage control training, all participants will be given a questionnaire to evaluate comfort level, self-efficacy, and other questions relating to hemorrhage control response.

7) Sample size calculation:

- a) Sample Size calculation was done for paired comparisons with 80% power and Bonferroni corrected for 4 pairwise comparisons for an alpha level of 0.0125 and correlation of 0.1. The largest difference was then taken as the sample size for each arm.
- b) The expected corrected proportions for the different tourniquets are:
 - (1) CAT: 80-90% (Control)
 - (2) RAT: 10-30%
 - (3) SWAT-T: 10-30%
 - (4) Sof-T: 20-40%
 - (5) Improvised: < 10%
- ii) The smallest presumed difference in correct application for the CAT (control) at 80% is to the Sof-T at 40%. To attain 80% power with alpha of 0.0125 the required minimum sample size is 34.
- c) All sample size calculations performed using Stata v14.1.

8) Statistical Analysis:

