- a) Paired statistical tests using McNemars test will be used for the univariate analysis of the primary outcome of correct tourniquet application comparing the CAT tourniquet as a control (CAT being type of tourniquet taught in the B-Con course) to each of the other tourniquet types (RAT, SWAT-T, Sof-T, Improvised) for 4 total pairwise comparisons.
- b) Descriptive statistical analysis (ANOVA, Kruskal-wallis, Mann Whitney U test, Student T-test) will be used to assess the secondary outcomes of time to tourniquet application, estimated blood loss prior to tourniquet application, and pressure applied by the tourniquet.
- c) Multiple Logistic regression will be used to assess for predictors of correct tourniquet application for each of the different tourniquet types. The model will include age, gender,

education level, any prior hemorrhage control training, and success in application for each of the other tourniquet types.

- d) Descriptive statistics will also be used to assess participants responses on the questionnaires. Non-parametric statistical tests (Wilcoxon signed rank test and generalized estimating equations) will be used to assess 5-point Likert scale questions.
- e) P-value for significance will be set at 0.05 after Bonferroni correction.

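### Section 8(c) fits five logistic models with at least 8 slopes each; at the stated minimum of 34, about 3 of 5 have no finite fit at the plan's most favourable rates and over 4 of 5 at mid-range rates

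*Combined protocol and SAP*

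**What the plan says.** Section 8(c) of the combined protocol and SAP states: "Multiple Logistic regression will be used to assess for predictors of correct tourniquet application for each of the different tourniquet types". Each model contains age and gender, then "education level, any prior hemorrhage control training, and success in application for each of the other tourniquet types". It names no penalised or exact method, gives no rule for separation or empty cells, and does not call the analysis exploratory. Section 8(e) sets one significance threshold without saying whether it covers 8(c).

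Section 7(a) says: "Sample Size calculation was done for paired comparisons with 80% power and Bonferroni corrected for 4 pairwise comparisons". It puts the corrected alpha at 0.0125 and assumes a correlation of 0.1. Section 7(b)(ii) concludes: "To attain 80% power with alpha of 0.0125 the required minimum sample size is 34". Nothing in section 7 sizes the regressions.

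The expected success rates in section 7(b) are CAT 80-90%, RAT 10-30%, SWAT-T 10-30% and Sof-T 20-40%; the last entry reads "Improvised: < 10" (per cent). Under section 3(b) every participant is tested on all five devices, so each model has one row per participant. Section 3(a) adds "The training takes place in groups of 20 to 50 at a time", so enrolment could exceed 34, but no planned total appears.

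**The concern.** Each model asks for at least 8 slopes: four participant characteristics (education counted as one term) and four other-device successes. With about 34 rows and outcomes that are rare in one direction, there are too few events to estimate them.

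The other-device indicators make it worse because they are sparse themselves. Few participants are expected to succeed with the improvised device or to fail with the CAT. When all the participants in such a small group share the same outcome on the modelled device, the maximum-likelihood odds ratio is infinite.

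The analyst would then meet infinite odds ratios, dropped observations or non-convergence, and would have to choose a remedy after seeing the data. Models that do converge would be heavily overfitted, so any reported predictors of correct application would be unreliable.

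**Working it through.** **1. The plan's own figure.** Inputs from section 7: CAT 80%, Sof-T 40%, alpha 0.0125 (taken as two-sided), power 80%, correlation 0.1.

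- Joint success: p11 = 0.8 x 0.4 + 0.1 x sqrt(0.8 x 0.2 x 0.4 x 0.6) = 0.340. Hence p10 = 0.460, p01 = 0.060 and d = 0.40.
- n = [z(1 - alpha/2) x sqrt(p10 + p01) + z(power) x sqrt(p10 + p01 - d²)]² / d² = 33.3, rounded up to 34.

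So 34 reproduces as a number of participants for the paired CAT versus Sof-T comparison.

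**2. Expected minority-class events per slope at N = 34.** Events = 34 x planned rate (failures for CAT, successes otherwise), divided by 8 slopes. This step uses only section 7 rates and counts education as a single term.

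| Model | Events | Per slope |
|---|---|---|
| CAT (failures 10-20%) | 3.4-6.8 | 0.43-0.85 |
| RAT, SWAT-T (10-30%) | 3.4-10.2 | 0.43-1.28 |
| Sof-T (20-40%) | 6.8-13.6 | 0.85-1.70 |
| Improvised (under 10%) | under 3.4 | under 0.43 |

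**3. How often a model has no finite fit.** Five correlated binary outcomes were simulated, and each 8-slope model was tested for complete or quasi-complete separation by linear programming. A constant outcome counted as no fit; constant covariates were dropped first.

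- Success rates for CAT/RAT/SWAT-T/Sof-T/improvised: favourable 80/30/30/40/9%; mid-range 85/20/20/30/5%.
- Assumptions not in the documents: latent correlation 0.17 (outcome correlation 0.06-0.10), normal age, 50% gender split, three-level education as one linear term, prior training 20% or 50%, no participant effects.
- Simulated trials per scenario: 1000 at N = 34, falling to 300 at N = 170. The simulation standard error of the averages is at most 0.07. Ranges below cover the two prior-training values.

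| N | Average models of 5 with no finite fit, favourable | Mid-range |
|---|---|---|
| 34 | 3.2-3.4 | 4.3-4.5 |
| 50 | 2.2-2.3 | 3.9 |
| 68 | 1.4-1.6 | 3.2-3.3 |
| 100 | 0.9-1.0 | 2.3-2.6 |
| 170 | 0.3-0.4 | 1.4 |

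The chance that at least 3 of 5 fail is 69-75% (favourable) and 94-96% (mid-range) at N = 34, and 39-44% and 88% at N = 50. By model, at N = 34 and favourable rates: CAT 82-84%, RAT and SWAT-T 52-58%, Sof-T 43-49%, improvised 90-93%.

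**4. Cause.** Average failures at N = 34 after removing covariates:

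| Covariates removed | Favourable | Mid-range |
|---|---|---|
| Improvised success | 2.0-2.4 | 3.6-3.8 |
| Improvised and CAT success | 1.3-1.8 | 2.5-2.9 |
| All four other-device successes | 0.7-1.3 | 1.3-2.0 |

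**5. Sensitivity at N = 34.** A separate simulation with improvised at 10% in the favourable set, outcome correlation 0 to 0.1, prior training 20-50%, and constant covariates counted either as failures or dropped gives 3.0-3.5 (favourable) and 4.4-4.75 (mid-range). At favourable rates, prior training at 10% raises the figure to 3.8-3.9, and a between-device correlation of 0.3 raises it to about 4.5. Even with all four other-device terms removed, the improvised model fails in 52-87% of runs, from favourable to mid-range rates.

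**6. Models that do converge.** In 300 simulated trials at N = 34 and favourable rates (CAT, RAT, SWAT-T, Sof-T), with no true participant effects, mean apparent AUC is 0.77-0.81 against 0.50-0.53 in 20,000 new simulated participants. With a real age effect (age alone gives AUC 0.67-0.68), it is 0.81-0.83 against 0.57-0.60.

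**The case against.** **Size.** Section 7(a) speaks of a sample size for each arm, and 34 is a minimum. If it meant 5 x 34 = 170 people, failures fall to 0.3-0.4 and 1.4 of 5. But every participant tests all five devices and 34 reproduces as a paired calculation, so 34 people is the natural reading. It stands that the size of the problem depends on enrolment, which the plan should state. One full training group of 50 would still lose about 2 models at favourable rates and almost 4 at mid-range.

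**Overfitting measure.** Section 8(c) looks for predictors and proposes no prediction score, so AUC is an indirect measure. In finite 8-slope fits with no true effects, 5% Wald tests of the participant covariates rejected in 3.6-4.6% of cases. So there is no excess of false positives per coefficient, and none is claimed here. The harm is instability: the median absolute gender log odds ratio was 0.8-0.9 when the truth was zero.

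**Assumed inputs.** Covariate distributions are not in the documents, and the ranges in step 3 vary only prior training. Step 5 shows a wider spread with the same conclusion. The events per slope do not depend on these assumptions.

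**Remedy.** Removing other-device success gives up something 8(c) asks for. Firth models that kept those terms (RAT, SWAT-T and Sof-T) did converge, but the intervals for improvised success ran about 29- to 117-fold either side of the estimate. Little is lost by moving that question to 2x2 tables.

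**Importance.** The analysis is not the primary one, and outright failure is usually visible to the analyst. Both points are fair. They limit the severity but do not supply a prespecified response.

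**Conclusion.** The concern holds: 8(c) is wrong as written for a trial at or near its stated size, and it should be fixed. The events per slope, at most 1.7 and under 0.43 for improvised, follow from the plan's own rates, N = 34 and the minimum slope count. The failure counts, about 3 of 5 at the most favourable rates and over 4 of 5 at mid-range, also rest on the assumed covariate distributions and on a between-device correlation near the plan's 0.1. Across the sensitivity checks the favourable figure runs from 3.0 to about 4.5. At favourable rates the problem is small by N = 170; at mid-range rates more than one model is still lost there. The McNemar comparisons in 8(a) are untouched.

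**What to change.** Reword section 8(c) as follows.

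1. For CAT, RAT, SWAT-T and Sof-T, fit device-specific logistic models with Firth-type penalisation on pre-test covariates only (age, gender, education as one term, prior training), with profile-likelihood confidence intervals.
2. Report the improvised device descriptively.
3. Report between-device association of success from paired 2x2 tables. There are 10 device pairs, and 4 of the tables are already needed for McNemar's test.
4. Label the analysis exploratory.
5. State the planned enrolment if it exceeds 34.

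A pooled model clustered by participant could be an optional sensitivity analysis only, because it assumes common covariate effects across devices.

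The cost is SAP wording. The other-device association would no longer be adjusted for participant characteristics, and precision stays poor. With 4 slopes at N = 34, events per slope are 0.85 (3.4/4) to 3.4 (13.6/4) for the four modelled devices. In 400 simulated trials per scenario the penalised models converged in 99.7-100%, but the median standard error of the gender log odds ratio was 0.79-1.02. A 95% interval therefore extends by a factor of exp(1.96 x 0.79) = 4.7 to exp(1.96 x 1.02) = 7.4 either side of the estimate, which is why the exploratory label is needed.

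### Section 8c treats success on the other four devices as predictors, although these are parallel outcomes; adjusting for them changes what the age, gender, education and prior-training coefficients measure

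*Combined protocol and SAP*

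**What the plan says.** Section 8c (Statistical Analysis) states the aim: "Multiple Logistic regression will be used to assess for predictors of correct tourniquet application for each of the different tourniquet types". It then lists the covariates: "The model will include age, gender", followed by "education level, any prior hemorrhage control training, and success in application for each of the other tourniquet types". So each of the five models has four baseline covariates and four indicators of success on the remaining devices.

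Section 3b describes the testing, in an order set by random allocation: "Participants will be tested in all 5 types of tourniquets sequentially using the same method but with the order of testing varying according to the" [...]. Section 4a adds: "Permutated block randomization will be used to vary the order for application of the 5 different types of tourniquets". The sequences themselves are not listed. Section 3b also says: "No feedback will be given to the participant throughout the testing process".

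Section 8c does not limit the other-device results to tests done earlier, and it describes no model without them. The documents give no expected effect sizes for age, gender, education or prior training. The only figure for within-person dependence is in the sample size section (7a): "Bonferroni corrected for 4 pairwise comparisons for an alpha level of 0.0125 and correlation of 0.1".

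**The concern.** There are two separate difficulties.

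The first is the label. Because all five devices are tested in varying order, a result on another device precedes the outcome for some participants and follows it for others, yet the model treats both alike. A result obtained after the outcome is not a predictor of it in the ordinary sense.

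The second does not depend on timing. Success on another device is a further outcome of the same person after the same course. If age, education or prior training acts through a general skill, the other-device results carry part of that skill. Holding them fixed removes part of the association the model is meant to describe. If a covariate acts on one device only, the distortion takes another form.

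At stake is the reading of the secondary results. A report could say that education or prior training is unrelated to success when the model has only shown that it adds little once the other devices' results are known. No model in 8c gives the overall association.

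**Working it through.** **The plan's own figure.** The documents give no figure for the regression, so the check starts with the paired sample size, which supplies the correlation used below.

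- Inputs (sections 7a and 7b): p1 = 0.80, p2 = 0.40, correlation 0.1, alpha 0.0125 (two-sided assumed), power 80%.
- Both succeed: 0.80 × 0.40 + 0.1 × √(0.80 × 0.20 × 0.40 × 0.60) = 0.3396. Discordant cells: 0.4604 and 0.0604, sum 0.5208. Difference d = 0.40.
- n = [2.498 × √0.5208 + 0.842 × √(0.5208 − 0.16)]² / 0.16 = 33.29, rounded up to 34. This matches the plan.

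**Timing.** Assume that each device is equally likely to hold each of the five positions.

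- For a given outcome device, the number of other devices tested later is 0, 1, 2, 3 or 4, each with probability 0.2. The mean is 2 of 4.
- The probability of at least one later result is 1 − 0.2 = 0.8. At the minimum sample size, 0.8 × 34 = 27.2, or about 27 participants in each model.
- Averaged over the five models the mean of 2 needs no assumption: in any sequence the counts of later results are 4 + 3 + 2 + 1 + 0 = 10, and 10/5 = 2. Balance is needed only to apply it to each model singly.

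**Effect of the adjustment.** These are large-sample simulations (400,000 participants) that compare a covariate's log odds ratio with and without the four other-device terms. They contain no test order, so nothing in them is due to timing. All covariate effects are assumptions.

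*Covariate acting through a shared skill.* One normal skill factor underlies all devices; success rates are 0.85, 0.20, 0.20, 0.30 and 0.05; the covariate explains 25% or 50% of the factor.

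| Factor variance | Mean phi | Shrinkage, 25% share | Shrinkage, 50% share |
|---|---|---|---|
| 0.2 | 0.087 | 19-26% | 14-19% |
| 0.3 | 0.13 | 25-34% | 19-27% |

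*Covariate acting alike on all devices, with skill shared beyond it.* Success-rate settings are 0.80, 0.20, 0.20, 0.40 and 0.08; prior training in 30% with probit effect +0.5; age −0.2 per SD. The columns give the prior-training log odds ratio with the terms divided by that without them.

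| Shared-skill variance | Phi, CAT with Sof-T | CAT model | Sof-T model |
|---|---|---|---|
| 0 | 0.047 | 0.996 | 0.999 |
| 0.1 | 0.097 | 0.840 | 0.845 |
| 0.2 | 0.146 | 0.734 | 0.738 |
| 0.4 | 0.24 | 0.609 | 0.584 |
| 0.6 | 0.33 | 0.552 | 0.492 |

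In the second row the CAT odds ratio for prior training falls from 2.45 to 2.12.

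*Prior training helping only CAT.* With shared-skill variance 0.2 and 0.4, the CAT log odds ratio becomes 1.02 and 1.07 times its unadjusted value. A null Sof-T effect moves to an odds ratio of 0.95 and 0.89. In the same CAT models the age coefficient, which acts on all devices, falls to 0.75 and 0.63 of its value.

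*Opposite effects.* If training helps CAT (+0.5) and hinders the others (−0.3), with shared-skill variance 0.2, the CAT coefficient rises by about 18%.

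**The case against.** Four arguments can be made for the plan.

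**The aim is exploratory.** Section 8c claims no causal or total effect, and predictor is often used to mean an associated factor. A mutually adjusted model estimates association given performance on the other devices, which is a legitimate quantity. This stands in part: a changed coefficient is biased only if read as the overall association. But 8c offers no model that gives that association, and it lists baseline and other-device terms together without saying that the estimates are conditional.

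**Timing does no demonstrated harm.** A reader might infer that the later results cause the shrinkage. The documents do not support that. Without carry-over, a result from before or after the outcome carries the same information; no feedback is given during testing, and nothing in the documents quantifies carry-over. The timing argument bears on the label, not on the size of any coefficient.

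**Shrinkage is not general.** A reader might also infer that the baseline effects are always pulled toward no effect. That needs skill shared across devices and a covariate acting similarly on them. Section 8a says CAT is the device taught in the course, so an effect of prior training specific to CAT is plausible, and there the CAT coefficient moves slightly the other way.

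**The shift is small beside sampling error.** At correlation about 0.1 the CAT log odds ratio moves by 0.897 − 0.753 = 0.144. With 34 participants, 80% success and 30% previously trained, the approximate standard error is 1/√(34 × 0.16 × 0.21) = 0.94, so the shift is about 0.15 standard errors. This stands for a trial at the stated minimum. It does not justify the four terms, which also take up scarce information: with at least 8 parameters, 34 × 0.20 = 6.8 expected CAT failures give 0.85 per parameter, against 1.7 with 4.

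**Conclusion.** The point holds in a limited form. Other-device successes are co-outcomes, and on average half of them are recorded after the outcome (for each single model, if orders are balanced), so they should not be called predictors. Independently of timing, including them means that the age, gender, education and prior-training coefficients no longer measure overall association with success.

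The direction and size of the change depend on assumptions that the documents do not settle. It is shrinkage of about 14-26% on the log odds ratio under shared skill at a correlation near 0.1, and more at higher correlation. It is under 1% with no shared skill. If prior training helps only CAT, it is a rise of a few percent for CAT, with a spurious Sof-T odds ratio of about 0.89-0.95.

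The matter is confined to a non-primary analysis. The McNemar comparisons in 8a and the sample size in section 7 are untouched. It is worth correcting because the correction is cheap.

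**What to change.** Amend section 8c as follows.

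- Make the main model for each device baseline-only: age, gender, education level and prior hemorrhage control training.
- Report success across devices separately as association: the 5 × 4 / 2 = 10 pairwise 2×2 tables, each with phi or an odds ratio, and without the word prediction.
- If carry-over is of interest, use only results from devices tested earlier in that participant's sequence.
- The planned eight-term model may be kept as a supplementary analysis, labelled as conditional association.

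The cost is SAP wording; data collection and the primary analysis do not change. The downside is that the main model no longer gives mutually adjusted odds ratios for other-device success, and the pairwise tables show that association unadjusted. The supplementary model recovers the adjusted figures if they are wanted.

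### Optional gain: Holm's step-down in place of Bonferroni for the four primary McNemar tests adds power for CAT versus Sof-T at no cost in participants, by about 12 points in the case the plan sized for and about 1 point at the range midpoints

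*Combined protocol and SAP*

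**What the plan says.** Section 8(a) sets out the primary analysis: "Paired statistical tests using McNemars test will be used for the univariate analysis of the primary outcome", with CAT as control against RAT, SWAT-T, Sof-T and the improvised tourniquet, "for 4 total pairwise comparisons". Section 8(e) gives the decision rule: "P-value for significance will be set at 0.05 after Bonferroni correction".

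Section 7(a) sizes the study on the same rule, "Bonferroni corrected for 4 pairwise comparisons for an alpha level of 0.0125 and correlation of 0.1". Section 7(b) gives expected rates of correct application: CAT 80–90%, RAT and SWAT-T 10–30% each, Sof-T 20–40%, improvised below 10%. Section 7(b)(ii) takes CAT at 80% against Sof-T at 40% as the smallest expected gap and concludes: "To attain 80% power with alpha of 0.0125 the required minimum sample size is 34".

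By section 3(b) every participant applies all five devices, so all four tests share the same CAT results. The plan mentions no step-down procedure. It does not state whether the tests are two-sided or which version of McNemar's test (uncorrected, continuity-corrected or exact) will be used.

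**The concern.** The plan's control of multiplicity is sound and consistent across sections 7(a), 7(b)(ii), 8(a) and 8(e). The question is whether it gives away power that it could keep for nothing.

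Single-step Bonferroni tests CAT versus Sof-T at 0.0125 even when the other three comparisons have already been rejected. On the plan's own expectations those three gaps are larger, so Sof-T will usually have the largest of the four p-values. Holm's procedure would then test it at 0.05. What is at stake is the power of the comparison with the least to spare, which is also the one that fixed the sample size.

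**Working it through.** **Inputs.** From section 7: four comparisons, alpha 0.05/4 = 0.0125, correlation 0.1, CAT 80%, Sof-T 40%, power 80%, n = 34. Assumed, because the plan does not fix them:

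- two-sided tests (these give the plan's 34; one-sided gives 29);
- RAT and SWAT-T at 30% and improvised at 10% in the limiting case (the top of each range; the plan says below 10% for improvised);
- correlation 0.1 between every pair of devices;
- for other CAT/Sof-T rates, RAT and SWAT-T at 20% and improvised at 10%.

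**1. Reproduce n = 34.**

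- Both correct: p11 = 0.8 × 0.4 + 0.1 × √(0.8 × 0.2 × 0.4 × 0.6) = 0.3396.
- Discordant cells: 0.8 − 0.3396 = 0.4604 and 0.4 − 0.3396 = 0.0604. Their sum is pd = 0.5208 and their difference is d = 0.40.
- n = [z(1−α/2)·√pd + z(power)·√(pd − d²)]² / d² = [2.498·√0.5208 + 0.842·√0.3608]² / 0.16 = 33.3, so 34. The plan's figure is confirmed.

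**2. Formula power at n = 34**, from Φ{[d√n − z(1−α/2)·√pd] / √(pd − d²)}, at the four Holm thresholds:

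| Alpha | 0.0125 | 0.0167 | 0.025 | 0.05 |
|---|---|---|---|---|
| Power, 80% v 40% | 81.1% | 84.3% | 88.3% | 93.7% |

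The first column is Bonferroni. The last is the most Holm can give, when the other three comparisons are already rejected.

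**3. Full step-down.** Under the same normal approximation, 2,000,000 draws of the four correlated differences give Holm power of 93.2% for Sof-T, a gain of 93.2 − 81.1 = 12.1 points. The chance of a miss falls from 18.9% to 6.8%. With RAT/SWAT-T/improvised at 20/20/5% or 10/10/5%, Holm power is 93.6% to 93.7%.

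**4. Actual tests, other rates and larger n.** Five correlated binary outcomes were simulated (300,000 trials for the limiting case and the error rates, 100,000 elsewhere). Each entry is CAT versus Sof-T power, Bonferroni → Holm:

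| Case | Formula | Uncorrected McNemar | Exact McNemar |
|---|---|---|---|
| 80 v 40, n = 34 | 81.1 → 93.2% | 86.0 → 95.1% | 77.9 → 92.0% |
| 80 v 40, n = 40 | 88.7 → 96.7% | 92.2 → 97.8% | 87.8 → 96.1% |
| 80 v 40, n = 50 | 95.6 → 99.1% | 97.1 → 99.4% | 95.4 → 98.8% |
| 80 v 40, n = 60 | 98.5 → 99.7% | 99.1 → 99.9% | 98.4 → 99.7% |
| 85 v 40, n = 34 | 91.7 → 98.1% | 95.0 → 98.8% | 90.8 → 97.9% |
| 80 v 30, n = 34 | 96.0 → 99.3% | 97.9 → 99.6% | 95.7 → 99.2% |
| 85 v 30, n = 34 | 98.9 → 99.9% | 99.6 → 99.96% | 99.0 → 99.9% |

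For 80 v 40 at n = 34 the continuity-corrected test goes from 76.3% to 90.9%. If only Sof-T differs and all other devices are at 80%, Holm adds nothing visible: 86.0% and 86.0% uncorrected, 77.9% and 77.9% exact.

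**5. Correlation.** For 80 v 40 at n = 34, the largest possible formula gain (alpha 0.05 against 0.0125) is 14.6 points at correlation 0, 12.6 at 0.1, 10.2 at 0.2, 7.7 at 0.3 and 5.1 at 0.4.

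**6. Error control.** Holm's first threshold equals Bonferroni's and the later ones are larger, so no Bonferroni rejection can be lost. Simulated Holm family-wise error (uncorrected; exact):

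- all five devices at 80%: 3.4%; 1.7%
- only Sof-T equal to CAT: 4.2%; 2.1%
- only Sof-T different from CAT: 3.3%; 1.7%

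All are below 5%.

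**The case against.** The strongest reply is that there is no defect. Bonferroni is valid, it is stated consistently, and on the plan's own formula it meets the 80% target with 81.1%. Choosing between two valid methods is the sponsor's right. That stands, and it is why this is only a suggestion.

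The 12 points also belong to one corner of the expected ranges, with CAT at its lowest and Sof-T at its highest. At 80 v 30 the gain is about 3 points and at the midpoints about 1. It shrinks if correlation or enrolment is higher than assumed, and section 7 gives a minimum rather than a target. Nor is 12 the exact gain of any particular test: it is about 9 points for the uncorrected test and 14 to 15 for the exact and continuity-corrected ones. All of this is true and limits the size of the benefit. The gain still never turns negative, and the corner is the case the plan itself chose to protect.

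There is a trade-off. If Sof-T truly equals CAT while the other three differ, the chance of a false Sof-T finding rises from about 1.0% to 4.2% (uncorrected) or 0.5% to 2.1% (exact). Matching simultaneous confidence intervals are also less simple under Holm. The first stays within the 5% family-wise limit the plan accepts, and the plan specifies no intervals.

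Finally, taking the four primary tests out of section 8(e) leaves that rule governing analyses with no stated number of tests, such as those that "will be used to assess the secondary outcomes of time to tourniquet application". That gap is already in the plan; the change neither creates nor closes it.

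**Conclusion.** The point holds as an optional improvement. Nothing in the plan is invalid, and n = 34 is right under the two-sided asymptotic formula. At the same family-wise error of 0.05, Holm is never less powerful than Bonferroni. For CAT versus Sof-T at n = 34 it adds about 12 points of formula power at 80% v 40% and about 1 point at 85% v 30%.

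The larger figure rests on correlation 0.1, exactly 34 participants, and the other three devices differing clearly from CAT, as the plan expects. It matters most if the exact or continuity-corrected test is used: with 34 participants, Bonferroni power in the limiting case is then 77.9% or 76.3%, below the 80% target, while Holm gives 92.0% or 90.9%.

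**What to change.** Before the data are seen, add to section 8(a):

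> For the primary outcome, the four McNemar p-values will be tested by Holm's step-down procedure at two-sided family-wise 0.05 (ordered p-values compared with 0.0125, 0.0167, 0.025 and 0.05, stopping at the first non-rejection), and Holm-adjusted p-values will be reported; this takes the place of the Bonferroni rule in 8(e) for these four tests only.

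Section 7 can stay as it is, since sizing at 0.0125 remains a valid and conservative basis. The wording of 8(e) is unchanged and continues to apply to 8(b) to 8(d). The cost is one sentence and no participants. A sponsor who values simple simultaneous intervals, or the lower error rate on Sof-T alone, may reasonably keep Bonferroni.
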